6.2 SECONDARY EFFICACY ANALYSES

6.2.1 Phase I and II: Change in IRLSS total score from baseline to Day 42 (Non-responders in Phase I Placebo group)

The change is defined as IRLSS total score at Day 42 minus IRLSS total score at baseline in each phase. The number of subjects, mean, median, standard deviation, minimum (min) and maximum (max) for the observed values, and change from baseline will be reported in summary table.

6.2.2 Phase I and II: Change in IRLSS total score from baseline to Day 42 (Non-responders in Phase I FCM group)

IRLSS total score from baseline to Day 42 between Phase I and Phase II will be summarized. The change is defined as IRLSS total score at Day 42 minus IRLSS total score at baseline in each phase. The number of subjects, mean, median, standard deviation, minimum (min) and maximum (max) for the observed values, and change from baseline will be reported in summary table.

6.2.3 Phase I and Phase II: CGI-I and PGI-I score at Day 42

The number (percentage) of subjects of each category will be summarized for CGI-I and PGI-I, separately.

6.2.4 Phase I and Phase II: Percentage of subjects who are much or very much improved at Day 42 as measured by the PGI-I

The number (percentage) of subjects who are rated as much or very much improved with the PGI-I on Day 42 will be summarized by treatment group (for Phase I only) for each treatment phase.

6.2.5 Phase I and Phase II: Change in sleep quality measured by MOS from baseline to Day 42

The actual value of MOS score on baseline and Day 42, and change from baseline to Day 42 will be summarized via descriptive statistics by treatment group (for Phase I only) for each treatment phase.

6.2.6 Phase I and Phase II: Number (percentage) of treatment non-responders at Day 42 of Phase I who respond to FCM in Phase II

The number (percentage) of treatment non-responders at Day 42 in Phase I who are turned into responders in Phase II, and the treatment responders of each phase, will be summarized by treatment group, separately. For Phase I, treatment differences in percentage will be assessed with the chi-square test, p-values will be presented. The subjects who missing responder/non-responder classification will be considered as non-responder.

6.2.7 Phase I and Phase II: Number (percentage) of treatment responders at Day 42

The number (percentage) of treatment responders at Day 42 of Phase I and Phase II will be summarized by treatment group in Phase I, separately. The subjects who missing responder/non-responder classification will be considered as non-responder.

6.2.8 Phase I and Phase II: Change in substantia nigra iron index from baseline to Day 42

The actual value of substantia nigra iron index on baseline and Day 42, and change from baseline to Day 42 will be summarized via descriptive statistics by treatment group (for Phase I only) for each treatment phase.

Substantia nigra iron index will be measured using MRI relaxation rate (R2*) or QSM.

6.2.9 Phase I and Phase II: Change in thalamus and motor cortex iron index from baseline to Day 42

The actual value of thalamus and motor cortex iron index on baseline and Day 42, and change from baseline to Day 42 will be summarized via descriptive statistics by treatment group (for Phase I only) for each treatment phase, separately.

Iron index will be measured using MRI relaxation rate (R2*) or QSM.

6.2.10 Phase III: Change in IRLSS total score from baseline to each visit

The actual value of IRLSS total score on baseline and each scheduled visit (i.e. Weeks 15, 25, 34, 43 and 52 via phone contact), and change from baseline to each scheduled visit will be summarized via descriptive statistics.

6.3 EXPLORATORY ANALYSES

6.3.1 Phases I and II: Vitamin D at each visit

The actual value of serum Vitamin D concentration on baseline, each post-baseline visit, and change from baseline to each post-baseline visit will be summarized via descriptive statistics by treatment group (for Phase I only) for each treatment phase.

A subject data listing of Vitamin D and phosphate for each visit will be provided.

6.3.2 Phases I and II: Change in thalamus and motor cortex iron index from baseline to Day 42 for other brain regions

The actual value of iron index in other brain regions (including caudate, putamen, nucleus accumbens, globus pallidus, subthalamic nuclei (STN), dentate and pulvinar) on baseline and Day 42, and change from baseline to Day 42 will be summarized via descriptive statistics by treatment group (for Phase I only) for each treatment phase, separately.

7. SAFETY ANALYSIS

All safety analyses will be performed on the Safety Population. No formal statistical testing will be performed for safety. Safety assessments include:

- Adverse events
- Laboratory assessments (hematology, iron indices, chemistry, and other)
- Vital signs

7.1 ADVERSE EVENTS

Adverse events (AEs) will be coded by System Organ Class (SOC) and Preferred Term (PT) using the Medical Dictionary for Regulatory Activities (MedDRA®, version 24.0 or higher). The verbatim term will be included in the AE listings.

A treatment-emergent adverse event (TEAE) is defined as an AE that occurs or worsens on or after the first dose of study drug in Phase I. Only TEAEs will be included in summary tables by treatment group (for Phase I only) for each phase. For AEs occurring on the first dosing day, if the start time cannot be ascertained, the event will be counted as treatment emergent. All AEs, treatment emergent or otherwise, will be presented in subject data listings.

The incidence of TEAEs will be summarized as the number (percentage) of subjects with TEAEs within SOC and PT by treatment group (for Phase I only) for each phase. Subjects who report the same PT on multiple occasions will be counted once for the PT: under the highest severity (severe > moderate > mild) when summarized by severity and under the closest relationship (probably related > possibly related > unlikely related > none) to study drug when summarized by relationship. If a subject reports multiple PT for a SOC, the subject will be counted only once for that SOC. Events with unknown severity or relationship will be counted as unknown.

TEAEs will be summarized as below.

- An overview table, including number of subjects with
 - TEAEs
 - serious AEs (SAEs)
 - study drug related TEAEs
 - study drug related SAEs
 - TEAEs by severity
 - TEAE of special interest (AESI)
 - TEAEs leading to study discontinuation
 - TEAEs leading to death
- TEAE by SOC and PT
- TEAE by SOC, PT, and Severity
- Study drug related TEAEs by SOC, PT
- SAEs by SOC and PT
- TEAEs leading to study discontinuation by SOC and PT

All TEAE tables will be sorted by SOC and PT in decreasing frequency of the number and percentage of subjects in the treatment group.

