8.2 Analysis Populations

The following analysis populations will be defined:

- Safety population: All subjects who receive randomized treatment.
 - Treatment Phase I Safety population: All subjects who receive randomized treatment.
 - Treatment Phase II Safety Population: All treatment non-responders in Treatment Phase I who receive FCM in Treatment Phase II.
 - Long-Term Extension Phase III Safety Population: All treatment responders in Treatment Phase I or Phase II who enter the Phase III assessment period.

- Treatment Phase I Full analysis set (FAS) population: All subjects who received randomized treatment and had a post-randomization measurement of the IRLSS and Clinical Global Impression performed by Investigator (CGI-I) in Phase I.
- Treatment Phase II FAS population: All subjects with a measurement of the IRLSS and CGI-I in Phase II.
- Long-Term Extension Phase III FAS population: All subjects in the Phase III Safety population with at least one telephone contact or treatment intervention during the Phase III assessment period.

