In **Treatment Phase III**, responders from either Treatment Phase I or Treatment Phase II will continue through into this 46-week long-term extension phase of the study, and be monitored and assessed by phone for RLS symptoms (IRLSS and HRSQ) and adverse events on Weeks 15, 25, 34, 43 and 52 (final follow-up visit) from treatment Phase I Day 0. During Phase III, subjects may receive additional unblinded treatments (i.e. a single FCM 750 mg undiluted slow IV push at 100 mg/minute) if at any time the subject reports worsening of RLS symptoms (an increase > 4 points on the IRLSS compared to the last evaluation captured for that subject) and laboratory criteria are met (ferritin < 300 ng/mL and a TSAT $< 45\%$). No additional treatment will be allowed after the Week 46. A final face-to-face study visit will occur on Week 52. If a clinic visit is not possible, final evaluation will be completed by phone.

The Schedule of Events for Phases I, II and III are presented as Table 1.1 and Table 1.2

Table 1.1 Schedule of Events Treatment Phase I and Treatment Phase II

STUDY VISIT PROCEDURES	SCREENING	Treatment Phase I and Treatment Phase II				
	-14	DAY 0	DAY 7+1	DAY 14+3	DAY 28+3 (PHONE CONTACT)	DAY 42+3
Informed Consent	X					X**
Eligibility	X	X				X
Medical History, including prior iron therapy	X	X				
RLS History	X	X				
D/C oral iron products	X					
Site contact IRT	X					
Physical exam	X					X
Vital Signs	X	X	X			X
Height and Weight without shoes	X					
CHDQ	X					
HTDI	X					
IRLSS	X	X			X	X
HRSQ		X				X
CGI-I						X
PGI-I						X
MOS Sleep Scale		X				X
Hematology	X	X	X	X		X
Iron Indices	X	X	X	X		X
Chemistry	X	X	X	X		X
Vitamin D		X	X	X		X
Erythropoietin		X				X
Trace Element		X				
Urine Pregnancy test	X					
Study Drug		X	X			
Brain MRI	X					X
Concomitant Meds	X	X	X		X	X
Adverse Events		X	X		X	X

** All Subject will be consented to participate in Treatment Phase II prior to any study procedures being completed

Table 1.2 Schedule of Events Long-Term Extension Phase III

STUDY VISIT PROCEDURES	Week 15 Phone Contact	Week 25 Phone Contact	Week 34 Phone Contact	Week 43 Phone Contact	Week 52 EOS
IRLSS	X	X	X	X	X
HRSQ	X	X	X	X	X
MOS / PGI-I					X
Concomitant Meds	X	X	X	X	X
Adverse Events	X	X	X	X	X
Physical Exam / VS	See protocol Section 6.6 for procedures for additional FCM dosing				
Iron Indices / Chemistries / Hematology					X
FCM Dosing					

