2. STATISTICAL METHODS

2.1 GENERAL CONSIDERATIONS

Analysis datasets will be produced according to CDISC standards. All study-collected data will be summarized in tables or graphs. Listing will be produced when appropriate and all ICH-required listings will be produced. In general, continuous variables will be summarized by number of subjects, mean, standard deviation (SD), median, minimum, and maximum values. Categorical variables will be summarized by number and percentage of subjects in each category.

In general, summary tables will present data by treatment group (for Phase I) and treatment phase.

Baseline definitions:

- Phase I: baseline (other than iron index) is the last non-missing value prior to receiving randomized study medication.
- Phase II: phase II baseline (other than iron index) is the last non-missing value prior to receiving unblinded FCM in Phase II.
- Phase I and Phase II: baseline for iron index measured by MRI is measured in screening.
- Phase III: phase III baseline is defined as Day 0 of Phase I for responders in Phase I and Day 0 of Phase II for responders in Phase II.

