7.1.1 Adverse Events of Special Interest

Adverse events of special interest include hypophosphatemia, hypersensitivity/anaphylactoid reactions, and injection/infusion site reactions. The search strategy will be identified as follows:

- TEAEs of hypophosphatemia by SOC and PT <Use the following MedDRA PTs to identify these TEAEs >
 - MedDRA PT Blood phosphorus decrease
 - MedDRA PT Blood phosphorus abnormal
 - MedDRA PT Hypophosphataemia
 - MedDRA PT Hypophosphataemic rickets
 - MedDRA PT Rickets familial hypophosphataemic
- TEAEs indicative of hypersensitivity/anaphylactoid reactions by SOC and PT
 - Hypersensitivity/anaphylactoid reaction search is based on the following search criteria: 2 SMQ (Anaphylactic reaction and Angioedema), and 1 PT of Hypersensitivity
- TEAEs of injection/infusion site reactions by SOC and PT <Use the following MedDRA PTs to identify these TEAEs >
 - MedDRA HLT Infusion site reactions
 - MedDRA HLT Injection site reactions
 - MedDRA HLT Administration site reactions NEC
 - MedDRA PT Infusion related reaction

The AEs of special interest will be summarized by SOP and PT.

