7.2 CLINICAL LABORATORY PARAMETERS

Laboratory assessments include hematology, clinical chemistry/ phosphorus, and iron indices:

- Hematology: Hgb, Hct, RBC, WBC, MCV, MCH, MCHC, RDW, platelets, differential count and reticulocyte count.
- Clinical chemistry: sodium, potassium, chloride, BUN, creatinine, albumin, alkaline phosphatase, total bilirubin, gamma-GGT, AST, ALT, LDH, calcium, phosphorus, glucose, bicarbonate and magnesium.
- Iron indices and Phosphorus: serum iron, serum ferritin, and total iron binding capacity (TIBC), percentage serum transferrin saturation (TSAT).

- Other: urine pregnancy (if indicated), other metals (serum copper and zinc), 1,25 dihydroxy vitamin D, 25 hydroxy Vitamin D (25OH-D) and erythropoietin.

All laboratory parameters will be presented in standard units. The actual value and change from baseline will be summarized by visit and treatment group (for Phase I only) using descriptive statistics.

The number and percent of subjects with treatment-emergent potentially clinically significant (PCS) laboratory values after baseline will be summarized by visit and treatment group (for Phase I only) for each phase. The denominator is all subjects with normal baseline and at least one post baseline assessment in the safety population of that phase and the numerator is the number of subjects with PCS (i.e., meets Grade III or Grade IV toxicity criteria from the National Cancer Institute Common Terminology Criteria) at post-baseline.

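### After Phase I, the SAP's TEAE and laboratory tables do not separate first from repeat FCM courses, or re-dosed from other subjects

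*SAP*

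**What the plan says.** The general layout rule in SAP 2.1 is: "In general, summary tables will present data by treatment group (for Phase I) and treatment phase". The safety sections follow it.

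- **Adverse events (SAP 7.1):** "Only TEAEs will be included in summary tables by treatment group (for Phase I only) for each phase". The sentence on incidence by SOC and PT repeats the restriction.
- **Laboratory values (SAP 7.2):** "The actual value and change from baseline will be summarized by visit and treatment group (for Phase I only) using descriptive statistics". Potentially clinically significant values "will be summarized by visit and treatment group (for Phase I only) for each phase".
- **Events of special interest (SAP 7.1.1):** "The AEs of special interest will be summarized by SOP and PT". No column grouping is stated. The overview table in SAP 7.1 includes these events, so they appear to follow the same layout.

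The phase-specific safety sets are in Protocol 8.2. Phase II is "All treatment non-responders in Treatment Phase I who receive FCM in Treatment Phase II". Phase III is "All treatment responders in Treatment Phase I or Phase II who enter the Phase III assessment period". On re-dosing, SAP 1.3.1 says: "During Phase III, subjects may receive additional unblinded treatments", provided that symptom and laboratory criteria are met.

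SAP 5.1 counts the subjects re-dosed in Phase III, but no adverse-event or laboratory table uses that count as a denominator. By contrast, SAP 6.2.1, 6.2.2, 6.2.6 and 6.2.7 report Phase II efficacy by Phase I arm.

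**The concern.** The Phase II and III safety populations are mixtures by exposure. In Phase II, an ex-placebo subject is on a first course (2 × 750 = 1,500 mg), while an ex-FCM subject is on a second (3,000 mg cumulative). In Phase III, the table covers subjects re-dosed, subjects with earlier FCM who are not re-dosed, and placebo responders with no FCM at entry. SAP 7.1 counts TEAEs from the first Phase I dose of study drug, placebo included, so events in the last group enter the same percentage.

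FCM safety is part of the primary objective for Phases I and II (SAP 1.1.1). The events of special interest are hypophosphatemia, hypersensitivity and injection or infusion site reactions, for which timing relative to an FCM dose matters. If a repeat course carried a different risk from a first, the planned tables would show only a blend.

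Phosphate raises a further question. Protocol 6.6 calls for it on Days 14 and 42 after a Phase III dose. Those days are not among the fixed Phase III visits in SAP Table 1.2, and SAP 2.3 tabulates scheduled visits only.

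**Working it through.** **The plan's own figures.** With 35 per arm and a two-sided 5% level, 50% versus 15% on the CGI-I gives 89.6% power (stated: above 85%). An IRLSS difference of 5.0 with SD 7.3 gives 80.6% by the t-test (stated: above 80%). Both hold. The same planning rates are used below only to size the pooled groups.

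**Inputs from the documents (SAP 1.3.3):** 35 per arm; CGI-I much or very much improved in 50% on FCM and 15% on placebo.

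**Assumptions:**
- The CGI-I rates stand in for the Responder rule, which also uses the IRLSS and the subject's request for treatment.
- All placebo Non-Responders meet the Phase II laboratory criteria, as do 25–100% of FCM Non-Responders.
- Phase II response is 50% in ex-placebo subjects and 0–50% in ex-FCM subjects.

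**Phase I outcome (expected numbers):**
- FCM: 35 × 0.50 = 17.5 Responders and 17.5 Non-Responders
- Placebo: 35 × 0.15 = 5.25 Responders and 29.75 Non-Responders

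**Phase II, second-course share w = 17.5e / (17.5e + 29.75), where e is the eligible fraction of FCM Non-Responders:**

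| e | Second course | Total | w |
|---|---|---|---|
| 100% | 17.5 | 47.25 | 37% |
| 75% | 13.125 | 42.875 | 31% |
| 50% | 8.75 | 38.5 | 23% |
| 25% | 4.375 | 34.125 | 13% |

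With first-course risk r1 and second-course risk r2, the pooled table shows r1 + w(r2 − r1). So only 13–37% of any difference between courses appears in it. For example, assumed risks of 5% and 20% give 5 + 0.370 × 15 = 10.6% at the top of the range and 5 + 0.128 × 15 = 6.9% at the bottom. Those risks are invented to show the mechanism.

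**Phase III entrants:**
- FCM Responders from Phase I: 17.5
- Placebo Responders from Phase I (no FCM at entry): 5.25
- Ex-placebo Phase II Responders: 0.5 × 29.75 = 14.875
- Ex-FCM Phase II Responders: 0 to 0.5 × 17.5 = 8.75
- Total: 37.625 to 46.375

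No-FCM share at entry: 5.25 / 46.375 = 11% to 5.25 / 37.625 = 14%.

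The documents give no re-dosing rate, so the share of Phase III subjects re-dosed cannot be sized from them.

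**The case against.** The best defence is that the data are reported, just not in this cut. SAP 7.1 lists all adverse events by subject, SAP 7.1.2 lists serious events, discontinuations and deaths, and SAP 6.3.1 lists vitamin D and phosphate by visit for Phases I and II. After early termination (SAP 9), actual groups may be small enough for listings to serve nearly as well. This stands as a limit: the information is missing from summary tables, not lost. It does not remove the point. A reader would have to rebuild the denominators by hand, and counts by course are more informative than a mixed percentage even when small. With descriptive reporting only, the split costs no power.

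A reader might draw four stronger inferences that the documents do not support.

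- **That no safety table reflects FCM exposure.** Phase I safety tables use the treatment actually received (SAP 2.2.2), and everyone in the Phase II set received FCM. What is missing is course number and re-dosing after Phase I.
- **That placebo responders in Phase III never receive FCM.** This holds only at entry; they may be dosed later.
- **That Phase III dilutes re-dosing risk several-fold.** That requires assuming almost no events in subjects not re-dosed. TEAEs of any cause are counted over many weeks, and the documents give no rates.
- **That Phase III follow-up differs greatly by route of entry.** Visits run to Week 52 from Phase I Day 0 (SAP 1.3.1), so for completers the planned difference is only about 6–7 weeks: 42 days of Phase II plus up to 7 days before it starts.

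On phosphate, SAP 2.1 promises that all collected data will be summarised, and SAP Table 1.2 refers to Protocol 6.6. Someone could therefore argue that the post-dose draws count as scheduled. The text does not settle this, so the values may, not will, be left out.

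**Conclusion.** The point holds as a gap in the summary tables, and closing it is a worthwhile, inexpensive improvement. The SAP text is explicit for TEAEs and laboratory values; for events of special interest the layout is inferred from SAP 2.1 and 7.1. The actual-treatment rule does not help, because the Phase II and III tables have no group column. Protocol 8.6 asks for TEAEs by treatment group without restricting this to Phase I, and SAP 9 does not list the restriction as a change.

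The size is illustrative: about 13–37% second-course subjects in the Phase II table and about 11–14% of Phase III entrants with no FCM. These figures rest on full planned enrolment, the CGI-I stand-in, and the assumed eligibility and Phase II response. The documents give neither actual enrolment nor event risks, so no amount of hidden risk can be stated.

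One caution: the phase-specific safety sets and the phosphate schedule come from the protocol text supplied, signed in April 2016, whereas the SAP refers to a protocol dated 4 September 2019. They should be confirmed against that version.

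**What to change.** - **Phase II:** present TEAE, special-interest and laboratory summaries by Phase I arm, labelled as first or second FCM course.
- **Phase III, re-dosed:** add a table of TEAEs and special-interest events from the first Phase III FCM dose onward, with re-dosed subjects as the denominator. Include the Day 14 and Day 42 post-dose phosphate values, and state in SAP 2.3 that these draws are tabulated.
- **Phase III, without re-dosing:** show events that occur without re-dosing separately, flagging subjects with no prior FCM.
- **SAP 7.1.1:** state the column grouping explicitly.

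This uses data already planned for collection and one derived exposure flag. The downside is smaller cells: at planned size the group with no FCM at entry would be about 5 subjects. Counts with denominators should therefore be shown beside any percentage, and the listings kept.

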7.1.1 Adverse Events of Special Interest

Adverse events of special interest include hypophosphatemia, hypersensitivity/anaphylactoid reactions, and injection/infusion site reactions. The search strategy will be identified as follows:

- TEAEs of hypophosphatemia by SOC and PT <Use the following MedDRA PTs to identify these TEAEs >
 - MedDRA PT Blood phosphorus decrease
 - MedDRA PT Blood phosphorus abnormal
 - MedDRA PT Hypophosphataemia
 - MedDRA PT Hypophosphataemic rickets
 - MedDRA PT Rickets familial hypophosphataemic
- TEAEs indicative of hypersensitivity/anaphylactoid reactions by SOC and PT
 - Hypersensitivity/anaphylactoid reaction search is based on the following search criteria: 2 SMQ (Anaphylactic reaction and Angioedema), and 1 PT of Hypersensitivity
- TEAEs of injection/infusion site reactions by SOC and PT <Use the following MedDRA PTs to identify these TEAEs >
 - MedDRA HLT Infusion site reactions
 - MedDRA HLT Injection site reactions
 - MedDRA HLT Administration site reactions NEC
 - MedDRA PT Infusion related reaction

The AEs of special interest will be summarized by SOP and PT.

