5.2 Study Drug Blinding/Administration

6.2.1 Study Drug Blinding

The treatment personnel who are not blinded will determine, through the IRT system, the treatment assignment on the day of treatment and will administer the appropriate treatment. The research coordinator will not know the subject's treatment, will not be present when the subject is treated, and will not have access to files indicating the treatment dose given. During IV treatment, the subject will be blinded to treatment administration (i.e. wear eye masks) to ensure minimal risk for detection of color differences between FCM and placebo treatments. All study personnel will be blinded to the iron indices and phosphorous (after randomization) throughout the study.

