5.2.1.1 Unblinded Personnel

The **unblinded study personnel** will be responsible for the following:

- Randomization of the subject on Day 0 through IRT system.
- Preparing, concealing, and administering the study drug on Day 0 (as Injectafer® is reddish-brown and slightly viscous).¹
- Completing the Study Drug Accountability Form, study drug dosing record and applicable CRF pages.
- Assessment of blinded laboratory parameters (iron indices and phosphorus).
- Retention of any source documents to which the Investigator and the site study team is blinded (i.e. dosing information).

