5.2.1.2 Blinded Personnel

The **blinded study personnel** will be responsible for all other study-related activities. During the period of study drug administration, the blinded personnel will not be present. However, the Principal Investigator or designee will be available in the event of an emergency and/or the need for adverse event assessment. All study personnel will be blinded to the post-treatment iron indices and phosphorous as the values may unmask the study assignment.

The blinding will be maintained in Phase I. In the event of an emergency that would require the Investigator to be aware of the treatment allocation prior to database lock, the Investigator can obtain this information, on a per subject basis, from the Sponsor's electronic database at the Investigative site. It is recommended to contact the sponsor's Medical Monitor or designee prior to unblinding. If a subject's treatment assignment is unblinded, the sponsor must be contacted immediately via [contact] Investigator Blinding

In addition to the above, the blinded investigator will be blinded to the IRLSS score and PGI-I score for each subject after randomization.

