6.7 Laboratory Assessments

Serum samples for laboratory analyses must be obtained at all appropriate visits and will be analyzed by the laboratory. All serum laboratory results will be provided to the physician for review and assessment. If the Investigator wishes to obtain a follow-up of an abnormal laboratory test, this test may be obtained after notification to the Sponsor. If a subject's phosphorous is below the LLN at the end of study participation the subject should return, as directed by the Investigator, for repeat phosphorous laboratory tests until the value is back WNL.

Hematology:	Hgb, Hct, RBC, WBC, MCV, MCH, MCHC, RDW, platelets, differential
	count, and reticulocyte count.

- Iron indices: serum iron, serum ferritin, and total iron binding capacity (TIBC), and percentage serum transferrin saturation (TSAT).
- Chemistry: sodium, potassium, chloride, BUN, creatinine, albumin, alkaline phosphatase, total bilirubin, gamma-GGT, AST, ALT, LDH, calcium, phosphorus, glucose, bicarbonate, and magnesium.

Other: urine pregnancy (if indicated), other metals (serum copper and zinc), 1,25 dihydroxy Vitamin D (1,25 [OH]₂D); 25 hydroxy Vitamin D (25OH-D) and erythropoietin.

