7.0 ASSESSMENT OF SAFETY

7.1 Adverse Events

Any untoward medical (clinical) event at any dose experienced by a subject during the course of this clinical trial, whether or not it is related to the investigational product, must be recorded on the Adverse Event page of the CRF.

For any laboratory abnormality, the physician will make a judgment as to its potential clinical significance. If the laboratory value is outside the safety limits and deemed a clinically-significant worsening from the baseline value, it should be considered an adverse event and should be recorded on the Adverse Events page of the case report form. If the laboratory value is outside the normal range, but not an adverse event, the Investigator should comment on the findings (i.e. "not clinically significant" or "unchanged from baseline") in the source documentation [laboratory report].

For the purposes of this study, worsening of RLS symptoms and low or high iron indices will not be considered adverse events. These values are reported in efficacy summaries.

To quantify the severity of adverse events the National Cancer Institute, NCI-Common Terminology Criteria for Adverse Events [CTCAE], Version 4.0 should be used to grade all events. These criteria are provided in the trial's study guide.

If a CTCAE criterion does not exist, the investigator should use Table 7.1.1 to assign the adverse event grade.

Grade	Adjective	Description
1	Mild	Asymptomatic or mild symptoms; clinical or diagnostic observations only; intervention not indicated.
2	Moderate	Moderate; minimal, local or noninvasive intervention indicated; limiting age-appropriate instrumental activities of daily living (i.e., preparing meals, shopping for groceries or clothes, using the telephone, managing money, etc.)
3	Severe	Severe or medically significant but not immediately life- threatening; hospitalization or prolongation of hospitalization indicated; disabling; limiting self care activities of daily living (i.e., bathing, dressing and undressing, feeding self, using the toilet, taking medications, and not bedridden.)
4	Life-threatening	Life-threatening consequences; urgent intervention

 Table 7.1.1
 Grading of Adverse Event Severity as per CTCAE v 4.0

		indicated.
5	Death	Results in Death due to the AE

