1.3.2 Randomization and Blinding

On Day 0 of **treatment Phase I**, all eligible subjects will be randomized via IRT system in a 1:1 ratio to receive a blinded dose of either FCM 750 mg undiluted slow IV push at 100 mg/minute or a Placebo (15 ml of Normal Saline) IV push at 2 ml/minute.

Other than designated randomization personnel, all subjects, investigators, and study conduct personnel are blinded to study drug assignment. The blinded investigators are also blinded to the IRLSS total score and PGI-I score for each subject after randomization. All study personnel will be blinded to the post treatment iron indices and phosphorous (after randomization) throughout the study.

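### The hypophosphatemia special-interest count in SAP 7.1.1 uses reported terms only while phosphorus is masked, so it may understate low phosphorus in Phase I and needs a laboratory count beside it

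*SAP*

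**What the plan says.** **How the event is counted.** SAP 7.1.1 names three special-interest groups: "Adverse events of special interest include hypophosphatemia, hypersensitivity/anaphylactoid reactions, and injection/infusion site reactions". For the first, the instruction is "TEAEs of hypophosphatemia by SOC and PT <Use the following MedDRA PTs to identify these TEAEs >", followed by five preferred terms. No laboratory criterion is attached.

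**How a low value becomes an event.** Protocol 7.1: "For any laboratory abnormality, the physician will make a judgment as to its potential clinical significance". The value must lie outside safety limits and be judged a clinically significant worsening. Protocol 7.1 excludes abnormal iron indices from adverse events altogether, but not phosphorus.

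**Who may see phosphorus.**
- Protocol 5.2, Study Drug Blinding: "All study personnel will be blinded to the iron indices and phosphorous (after randomization) throughout the study".
- Protocol 5.2.1.2: "All study personnel will be blinded to the post-treatment iron indices and phosphorous as the values may unmask the study assignment".
- SAP 1.3.2: "All study personnel will be blinded to the post treatment iron indices and phosphorous (after randomization) throughout the study".
- Protocol 5.2.1.1, among the duties of unblinded staff: "Assessment of blinded laboratory parameters (iron indices and phosphorus"; the same list gives them the applicable CRF pages.
- Protocol 6.7: "All serum laboratory results will be provided to the physician for review and assessment". Phosphorus is on that section's chemistry panel and no exception is made. The section also provides for repeat tests, directed by the Investigator, when phosphorus is below the LLN at the end of participation.

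**What else is reported.** SAP 7.2 summarizes actual values and changes by visit and Phase I arm. It counts subjects with Grade III or IV values by visit among those with a normal baseline. SAP 6.3.1 lists phosphate by subject and visit.

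**The concern.** The count depends on someone seeing a low value, judging it and writing a term. The masking rules in three places keep that value from study personnel, and blinded staff collect adverse events after dosing (Protocol 6.4.1). Day 14 in Phase I is a blood draw with no adverse-event assessment scheduled. A low phosphorus without symptoms may therefore never become a term.

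Phase I is the only placebo-controlled safety comparison, and the special-interest table is where a reader will look for this risk. SAP section 9 records that these events were added in the SAP, so the definition sits on top of event data collected under the masking rules. A row showing few or no events in either arm could be taken as no signal when it partly reflects who was allowed to see the results.

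**Working it through.** **1. Is there a plan figure to reproduce?** No. Neither document gives a hypophosphatemia rate, an expected count, or a chance that a low value is recorded. The only usable input is the planned arm size: 35 per group (SAP 1.3.3). SAP section 9 says the study ended early, so actual arms may be smaller.

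**2. Is the route from value to term defined?**

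| Step | Points to masking | Points to access |
|---|---|---|
| Who sees the value | Protocol 5.2, 5.2.1.2; SAP 1.3.2 | Protocol 5.2.1.1 (unblinded staff); 6.7 (physician) |
| Who judges it | Protocol 7.1: the physician, masked under the rules above | Protocol 6.7: the physician, with all serum results |
| Who records it | Protocol 5.2.1.2: blinded staff handle all other study activities | Protocol 5.2.1.1: unblinded staff complete applicable CRF pages; 7.2: events observed by study staff are recorded |

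Routes exist on paper, but they conflict. No section gives unblinded staff a threshold for action, a hand-off to the physician, or an explicit duty to open an adverse-event page.

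**3. How much could the term count differ from a laboratory count?** Let n = 35, r = true share of FCM subjects with an asymptomatic low value, and q = chance that such a value becomes one of the five terms. Both r and q are assumptions, varied over a range.

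- Expected laboratory count = n × r
- Expected term count = n × r × q
- P(term count ≤ 1) = (1 − rq)^n + n × rq × (1 − rq)^(n − 1)

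Example, r = 30% and q = 5%: rq = 0.015. The laboratory count is 35 × 0.30 = 10.5 and the term count is 35 × 0.015 = 0.53. P(≤ 1) = 0.985^35 + 35 × 0.015 × 0.985^34 = 0.589 + 0.314 = 0.903.

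| r | Expected laboratory count | Term count, q = 5% | P(≤ 1), q = 5% | P(≤ 1), q = 10% | Term count, q = 25% | P(≤ 1), q = 25% |
|---|---|---|---|---|---|---|
| 10% | 3.5 | 0.18 | 99% | 95% | 0.88 | 78% |
| 30% | 10.5 | 0.53 | 90% | 72% | 2.6 | 25% |
| 50% | 17.5 | 0.88 | 78% | 47% | 4.4 | 6% |
| 70% | 24.5 | 1.2 | 65% | 29% | 6.1 | 1% |

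At q = 0 the term count from asymptomatic values is zero at every r; at q = 1 it equals the laboratory count. The result turns on q, which the documents leave open. Expected counts fall in proportion if the arms are smaller than 35.

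**4. Do the other outputs supply the missing count?** In part. The Grade III/IV count in SAP 7.2 leaves out milder falls and subjects with an abnormal baseline. It is made visit by visit, so it does not give the number of subjects affected at any time. Values below the LLN but short of Grade III appear in means, medians, minima and the listing, but in no subject count.

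**The case against.** The strongest reply is that the phosphorus data are not hidden from the final report. SAP 7.2 gives values and changes by visit and Phase I arm, SAP 6.3.1 lists every subject, and severe falls are counted. A sparse special-interest row would sit beside those tables. That stands: a reader might infer that mild falls are lost to the study, and they are not. What is missing is a count of subjects.

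Second, a reader might infer that an asymptomatic low value has no route to the event page. The documents do not support that. Protocol 6.7 sends results to the physician, and its repeat-test provision presupposes that the Investigator learns of a low value at least at the end of participation. Protocol 5.2.1.1 and 7.2 give staff a possible route too. These provisions conflict with the masking rules, so the route is unsettled, not absent.

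Third, under Protocol 7.1 a value not judged a clinically significant worsening is not an adverse event, so omitting it from an event table follows the protocol's definition. That also stands. It is a reason to put a laboratory row beside the term count and keep the term count as it is.

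Fourth, one might expect the later, open-label phases to report more events through better ascertainment. That is speculative: Protocol 5.2 and SAP 1.3.2 say the masking to phosphorus lasts throughout the study.

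**Conclusion.** The concern holds in a limited form. The Phase I term count depends on an undefined recording process, may understate low phosphorus, and should not be read as incidence. The documents do not show that it will be near zero whatever the true rate. That reading needs a recording chance close to zero: at an assumed 25%, a true rate of 50% would give a count of 0 or 1 only 6% of the time. Symptomatic cases could also be reported despite masking.

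The size of the undercount cannot be determined. The table above rests on assumed rates, assumed recording chances and the planned arm size. This affects how a descriptive safety table is read; it leaves the efficacy analyses untouched.

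**What to change.** 1. In SAP 7.1.1, or in 7.2 with a cross-reference, add the number (%) of subjects with any post-dose phosphorus below the LLN, and with Grade III/IV, at any time in the phase. Show Phase I by arm. Denominator: subjects with at least one post-dose phosphorus value in that phase. State whether unscheduled values count, since SAP 2.3 limits tables to scheduled visits.
2. Keep the preferred-term count as a separate row, footnoted that reporting was affected by masking to phosphorus.
3. Reconcile Protocol 5.2, 5.2.1.1, 5.2.1.2 and 6.7 with SAP 1.3.2 on who sees phosphorus and how a low value reaches the adverse-event page. If data collection is over, describe in the SAP what was done in practice.

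The data already exist: chemistry, which includes phosphorus, is scheduled at Days 7, 14 and 42 after the first dose in Phase I. The cost is SAP wording and a small addition to one table. The reported figure may be higher than the term count, and it will include any subject already low at baseline, in either arm.
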